## 6.2.7 Intercurrent Events

**Table 5 Intercurrent Events**

Label	Intercurrent Event (IcEv) Type
IcEv1 (Death not due to COVID-19)	Death due to any cause other than COVID-19 associated.

IcEv2 (Non-study COVID-19 vaccine)	Use of non-study COVID-19 vaccine.
IcEv3 (Early infection)	Positive reverse transcriptase-polymerase chain reaction (RT-PCR) test or other COVID-19 positive test or seropositivity for anti-nucleocapsid antibody indicating exposure to SARS-CoV-2 prior to vaccination or SARS-CoV-2 infection prior to 7 days (inclusive) after the second study vaccination dose (Day 35).
IcEv4 (Study infection)	Develops virologically confirmed SARS-CoV-2 infection, with or without COVID-19 symptoms (Positive RT-PCR or other COVID-19 positive test or seropositivity for anti-nucleocapsid antibody indicating exposure to SARS-CoV-2) more than 7 days after second study vaccine dose ( $\geq$ Day 36). Additional details on how to define primary efficacy endpoint is presented in Section 6.4.
IcEv5 (Confounding On-study Medications)	Receives any of the following concomitant medications/vaccines prior to the time point for which the analysis is being performed: 
 
• Live vaccines within 28 days before or after any study vaccination
 
• Systemic (oral, intravenous, intramuscular or subcutaneous) corticosteroids given at any study time point prior to the timepoint at which the analysis is being performed
 
• Blood products or immunoglobulins given at any study time point prior to the timepoint at which the analysis is being performed
 
• Immunosuppressive medications, including cytotoxic medication for cancer or autoimmune disease, given at any study time point prior to the timepoint at which the analysis is being performed
 

Abbreviations: COVID-19=coronavirus disease 2019; IcEv=intercurrent event; SARS-CoV-2=severe acute respiratory syndrome coronavirus 2.

## 6.3 Study Population

### 6.3.1 Participant Disposition, Analysis Sets

Summaries of participant disposition will be prepared for all participants for randomized set, including the number and percent screened, randomized, and administered study vaccine at each dose. The reasons for screen failures and the number that withdrew from study treatment and from the study along with the reasons will be summarized and listed. Participant disposition will also be presented separately for Day 1 to Day 91 and Day 92 to EOS.

The reasons for exclusion from different analysis sets, and termination from study will be summarized and listed.

The number of participants in each analysis set will be summarized in the randomized set.

The summaries will be presented by vaccine group and overall. The denominator for all percentages will be the total number of participants in each vaccine group.

The following by-participant listings will be presented.

- Study completion information, including the reason for premature study withdrawal.
- Inclusion/exclusion criteria
- Inclusion in study analysis sets
- Protocol deviations
- Reasons for exclusion from the analysis set and if they completed the study.

Disposition table for Phase 3b SAS will be also produced by subgroups as specified in Section 6.2.5.

### **6.3.2 Demographic and Baseline Characteristics**

Baseline demographics and characteristics, including age, height, weight, sex, race, ethnicity, region of study sites, age group, risk group, and body mass index (BMI) will be summarized. These will be summarized for the mITT, SAS, RS and IAS by vaccine group and total of all participants. If the number of participants included in the PP analysis set or RAS analysis set is  $\geq 10\%$  different from mITT or the SAS, it will also be presented.

Demography table for Phase 3b SAS will be also produced by subgroups as specified in Section 6.2.5.

A listing of individual demographics will be provided.

Medical history data will be presented by System/Organ/Class (SOC) and Preferred Term (PT) for SAS.

### **6.3.3 Prior and Concomitant Medication**

Prior and Concomitant medications will be coded using the WHO Drug dictionary.

Prior medications will be defined as any medication with a start date before the date of first dose of study vaccine administration. If a medication date is missing, or partially missing, and it cannot be determined whether it was taken prior or concomitant to treatment, it will be considered a prior and concomitant medication.

Medications with a start date on or after the date of first dose of study vaccine administration and not after the last dose of study vaccine administration will be considered concomitant.

Medications taken prior to the first dose of study vaccine administration and continuing after the first dose of study vaccine administration will be considered both prior and concomitant.

Prior and Concomitant medications results will be tabulated by ATC and preferred term. The use of Prior and Concomitant medications will be included in by-participant data listing.

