6.8 Concomitant Therapies and Procedures

6.8.1 Concomitant Therapy

Study site staff must question the participant regarding any medications taken (including herbal/homeopathic substances) and vaccinations received by the participant. The following information will be recorded in the eCRF:

- All non-study vaccinations administered within the period starting 28 days before the first dose of study vaccine and for the duration of study participation.
- All concomitant medications and non-study vaccinations taken through 28 days after each study vaccination.
- Any concomitant medications/vaccines used to prevent or treat COVID-19.
- Any concomitant medications/vaccines relevant to or for the treatment of a solicited or unsolicited AE, an SAE, an MAAE, or an AE leading to discontinuation/withdrawal.
- Participants will be asked prior to vaccination and will be asked for 7 days after each vaccination of the initial series in the Diary if they have taken any antipyretic or analgesics to prevent or treat vaccine-associated side effects (AEs). For participants in Phase 2/3a, the diary will also be completed for 7 days after the 3rd dose of study vaccine (Day 92).

All medications and interventions necessary for the appropriate care of the study participant, particularly to treat COVID-19, should be administered and appropriately documented along with the AE.

All concomitant medications/vaccines must be recorded in the eCRF until 28 days after each dose of study vaccine. Thereafter, only vaccines and concomitant medications associated with an SAE, MAAE, or AEs leading to discontinuation/withdrawal will be entered in the eCRF.

Prohibited Concomitant Vaccines

Receipt of off-study COVID-19 vaccine is actively discouraged for enrolled participants. Any participant who receives an off-study COVID-19 vaccine will not receive further study vaccinations. All participants should remain in the study until the Final Visit (Day 394). If the off-study vaccine becomes known to the site prior to Switchover/Further Study Vaccine, the participant will not receive Switchover/Further Study Vaccine vaccinations and will be requested to stay in the study through Final Visit (Day 394).

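### The SAP's concomitant class stops at the last vaccine dose, so medication newly started after that date falls outside the prior and concomitant medication tables

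*SAP*

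**What the plan says.** SAP 6.3.3 (Prior and Concomitant Medication) sets up two classes.

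- **Prior:** "Prior medications will be defined as any medication with a start date before the date of first dose of study vaccine administration".
- **Concomitant:** the start must fall no earlier than the first dose, and the upper bound reads "and not after the last dose of study vaccine administration will be considered concomitant".

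Two further rules widen the concomitant class. A medication begun before the first dose "and continuing after the first dose of study vaccine administration will be considered both prior and concomitant". Where a date is missing or partial and "it cannot be determined whether it was taken prior or concomitant to treatment, it will be considered a prior and concomitant medication".

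The outputs are tied to these classes: "Prior and Concomitant medications results will be tabulated by ATC and preferred term", and "The use of Prior and Concomitant medications will be included in by-participant data listing". No third class, such as post-vaccination medication, is defined.

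Protocol 6.8.1 (Concomitant Therapy) asks for more to be recorded: "All concomitant medications and non-study vaccinations taken through 28 days after each study vaccination". After 28 days, recording narrows to medication linked to an SAE, an MAAE or an AE leading to discontinuation or withdrawal. A separate item in the same list covers anything used to prevent or treat COVID-19 and gives no end date.

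**The concern.** The protocol's window of 28 days after each dose includes the last dose, and the protocol calls what is taken in that window concomitant. The SAP's upper bound removes every new start in that window. SAP Section 7, which sets out departures from the protocol in detail, has no entry for this, so it looks unintended.

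The medication table also stops short of the safety tables it should support. SAP 6.6.1.2 summarises unsolicited AEs for 28 days after each dose, including Dose 4, and Dose 2 in Phase 3c. SAP 6.6.1.3 carries SAEs and MAAEs to the end of study. Events after the final dose would be tabulated, but treatment newly started for them would not. The diary does not fill the gap: SAP 7.2 records that antipyretic and analgesic use was not solicited on the diary card.

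**Working it through.** The plan states no figure for this, so there is nothing to reproduce. The check is a reading of the definition followed by a count of nominal days.

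**Step 1: classify by start date S**, with first dose F and last dose L.

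- S < F: prior, and also concomitant if it continues after F.
- F ≤ S ≤ L: concomitant.
- S > L, date known: neither.
- Timing undeterminable from a missing or partial date: both.

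The gap is the third line only.

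**Step 2: dosing days.** Doses 1 and 2 are on Days 1 and 29 in all phases. Doses 3 and 4 are on Days 92 and 120 in Phases 1, 2, 3a and 3b (Protocol 4.4, SAP 2.1). Phase 3c has no further doses. Participants in the other phases who fail the Day 92 criteria (Protocol 5.1.5) also stop at two.

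**Step 3: days in the all-medication window.** With k doses spaced at least 28 days apart, the window is 28 × k days. The rule omits the last 28, so the omitted share is 28 / (28 × k) = 1/k.

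| Participants | L | Window | Omitted | Share |
|---|---|---|---|---|
| Two doses (Phase 3c; others given no further vaccine) | Day 29 | Days 1–57: 28 + 28 = 56 | Days 29–57: 28 | 28/56 = 50% |
| Four doses (Phases 1, 2, 3a, 3b) | Day 120 | 56 + (Days 92–148: 28 + 28) = 112 | Days 120–148: 28 | 28/112 = 25% |

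**Step 4: later event-linked and COVID-19 medication.** To the final visit on Day 394, the time after the cut-off is 394 − 29 = 365 days for two-dose participants and 394 − 120 = 274 days for four-dose participants. A new start anywhere in that time is in neither class.

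**Step 5: who is in which row, as planned** (Protocol 4.1). Phase 3c is about 2,400 of 19,400, or 12%. The other phases total 100 + 300 + 600 + 16,000 = 17,000, or 88%, and are planned for four injections. The documents do not say how many of the 17,000 received no further vaccine.

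**Step 6: what the omitted window follows.** In Phases 1 and 3b the Day 120 injection is placebo for the initial ARCT-154 arm and the second ARCT-154 dose for the initial placebo arm. In Phases 2 and 3a it is likewise placebo for everyone who began on ARCT-154 and ARCT-154 for those who began on placebo. The lost window is therefore post-placebo in one arm and post-vaccine in the other. In Phase 3c it follows the second active dose in both arms.

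**The case against.** The strongest reply is that Protocol 6.8.1 governs collection, not analysis. Protocol 8.7 leaves data conventions to the SAP, and limiting the class to the dosing period is a possible convention. That stands as far as it goes, but a convention of that kind needs somewhere to put the remaining records and an entry in Section 7. The SAP has neither.

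Four stronger readings are tempting, and the documents do not support them.

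- **All medication taken after the final dose disappears.** It does not. Medication started on the last-dose date, started earlier and continued, or of undeterminable date still counts, and so do new starts after earlier doses.
- **Half of medication use is lost.** The percentages are calendar days, not use, and the documents give no usage data. The 50% applies only to two-dose participants.
- **Efficacy, immunogenicity or AE results are affected.** They are not. Confounding medication (IcEv5) and non-study COVID-19 vaccine (IcEv2) have their own definitions in SAP 6.2.7, and none of these analyses uses the 6.3.3 class. The events themselves stay in the AE tables, and Protocol 7.4.1.3 has required treatment recorded with each unsolicited AE.
- **Tables for two-dose and four-dose cohorts cannot be compared.** Phase 3c is reported separately (SAP 5.3), and both its arms have the same nominal cut-off. Unequal cut-offs arise within a table only from participants in the other phases who had no further doses, a group that cannot be sized from the documents.

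It also stands that for participants who receive the Day 120 dose, all new starts in the placebo-controlled period to Day 92 are captured. For those initially on ARCT-154, the lost window follows placebo.

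**Conclusion.** The point holds as a minor error in a stated rule. As written, the class leaves out every medication newly started, with a known date, after the last dose. That is 50% of nominal post-dose collection days for two-dose participants and 25% for four-dose participants, plus later event-linked and COVID-19 medication. The loss matters most where the final injection is active: Phase 3c after Dose 2, initial-placebo participants after their second ARCT-154 dose, and ARCT-154 recipients in the other phases who stopped at two doses. The consequence is an incomplete descriptive table and, read literally, an incomplete listing.

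This rests on three assumptions: nominal visit days, dosing as planned, and a literal reading of the last dose as the participant's last injection of any study vaccine, placebo included. The 6.3.3 wording supports the last of these, since it refers to study vaccine in general.

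**What to change.** In SAP 6.3.3:

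1. Define concomitant as started on or after the first dose, or ongoing at it, through 28 days after the participant's last dose.
2. Tabulate separately any later medication linked to an SAE, an MAAE, an AE leading to discontinuation or withdrawal, or COVID-19.
3. State that the by-participant listing contains all recorded medication, whatever its class.

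A separate post-vaccination class would also close the gap. If the sponsor prefers to keep the dosing-period definition, it needs that extra class and an entry in Section 7.

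The cost is a change of wording, one derivation flag and one added table. The protocol already requires these records in the eCRF, so no new data are needed.

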#### 6.3.4 Exposure and Compliance

Vaccine exposure and compliance are considered in analysis set definitions. The reasons a vaccine dose was delayed will be summarized.

Vaccine exposure table for Phase 3b SAS will be also produced by subgroups as specified in Section 6.2.5.

Participants receiving incorrect/unplanned treatment will be presented in a listing for planned versus actual treatment.

#### 6.3.5 Serostatus by SARS-CoV-2 nucleocapsid antibody test

Seropositivity status by SARS-CoV-2 nucleocapsid antibody test will be listed for the randomized set.

### 6.4 Efficacy Evaluation

Each efficacy evaluation will be performed for Phase 3b, Phase 1/2/3a, and Pooled (data from Phase 1/2/3a/3b) separately. Analysis will be performed on the mITT analysis set unless stated otherwise. Efficacy estimands are described in Section 9.2.2.

**Table 6 Overview of Efficacy Analysis**

Reference to Protocol Endpoints (a)	Endpoint/Event Description*	Analysis Set	Time at Risk**	Subgroups
Primary Exploratory 2 (Phase 1/2/3a)	First occurrence of confirmed, protocol-defined COVID-19 with onset between Day 36 and Day 92	mITT (3b & 1/2/3a & Pooled) PP (3b & Pooled)	[Last date at risk – (Date received 2nd dose + 7 days)]+1	Yes, for mITT (3b)
Secondary 1	Severe COVID-19 with onset between Day 36 and Day 92 inclusive	mITT (3b & 1/2/3a Pooled) PP (3b & Pooled)	[Last date at risk – (Date received 2nd dose + 7 days)]+1	Yes, for mITT (3b)

Reference to Protocol Endpoints (a)	Endpoint/Event Description*	Analysis Set	Time at Risk**	Subgroups
Secondary 2	COVID-19 with onset at any time after the first dose of study vaccine administration and up to Day 92	ITT + no prior infection (3b & 1/2/3a & Pooled)	[Last date at risk – Date received 1st dose]+1	No
Secondary 3	Death attributed to COVID-19 occurring between Day 36 and Day 92	mITT (3b & 1/2/3a & Pooled) PP (3b & Pooled)	[Last date at risk – (Date received 2nd dose + 7 days)]+1	Yes, for mITT (3b)
Secondary 4	COVID-19 with onset between Day 36 and Day 92	Participants with both doses of study vaccine and no infection between Day 1 and Day 35, but including those who are seropositive at baseline (Day 1) (3b & 1/2/3a & Pooled)	[Last date at risk – (Date received 2nd dose + 7 days)]+1	Yes, for 3b
Exploratory 1	Severe COVID-19 with onset at any time after the first dose of study vaccine administration and up to Day 92	ITT + no prior infection (3b & 1/2/3a & Pooled)	[Last date at risk – Date received 1st dose]+1	No
Exploratory 2	Death attributed to COVID-19 occurring at any time after the first dose of study vaccine administration and up to Day 92	ITT + no prior infection (3b & 1/2/3a & Pooled)	[Last date at risk – Date received 1st dose]+1	No
Exploratory 3	COVID-19 with onset at any time after the first dose of study vaccine administration and up to Day 92	ITT (3b & 1/2/3a & Pooled)	[Last date at risk – Date received 1st dose]+1	No

Reference to Protocol Endpoints (a)	Endpoint/Event Description*	Analysis Set	Time at Risk**	Subgroups
Exploratory 4a	COVID-19 with onset between Day 36 and Day 92 by specific variant	miITT (3b & Pooled)	[Last date at risk – Date received 1st dose]+1	No
Exploratory 4b	COVID-19 with onset at any time after the first dose of study vaccine administration and up to Day 92	ITT + no prior infection (3b & Pooled)	[Last date at risk – Date received 1st dose]+1	No
Exploratory 5a	Severe COVID-19 with onset between Day 36 and Day 92 by specific variant	miITT (3b & Pooled)	[Last date at risk – Date received 1st dose]+1	No
Exploratory 5b	Severe COVID-19 with onset at any time after the first dose of study vaccine administration and up to Day 92	ITT + no prior infection (3b & Pooled)	[Last date at risk – Date received 1st dose]+1	No

\*COVID-19 events will be confirmed, protocol-defined cases. \*\* Where the last date at risk will be defined as COVID-19-event date or censor date, whichever comes first.

(a) Unless specified otherwise, reference to the protocol endpoints is a reference to the Phase 3b endpoints.

Confirmed, protocol-defined COVID-19 cases will be determined by case report form (CRF) data, as confirmed by the blinded Independent Adjudication Committee and adjudicated for severity, with the date of case onset as date of symptom onset and date of positive COVID test date, whichever occurs first. Both protocol-defined and (protocol-defined) severe cases flagged in the CRF will be included in the primary endpoint.

For participants with no covid-event during the time interval the censor date for the last date at risk is whichever of the following comes first:

- Date of completion of Day 92 visit;
- Date of death unrelated to COVID-19;
- Date of receipt of Switchover or receipt of non-study COVID-19 vaccine
- Lost to Follow-up (last known alive date or date of Day 1+91 days, which is earlier).

Section 9.2.2 presents the endpoints and analyses in terms of estimands for primary, secondary and exploratory efficacy analyses.

As a sensitivity analysis of the primary endpoint (Phase 3b only), severe cases and deaths due to COVID-19 will be repeated using all COVID-19 cases from CRF, including those cases that are not confirmed by the blinded Independent Adjudication Committee and with severe or death severity as reported in the CRF.

Day 36 is defined as second dose+7 days (29+7=36 days), and Day 92 is defined as second dose+63 days (29+63=92 days). Another sensitivity analysis of the primary endpoint (Phase 3b only) will be performed using Day 92 visit instead of second dose+63 days.

COVID-19 cases confirmed by the blinded Independent Adjudication Committee will be presented as frequency table by time intervals of Day 1-Day 35 and Day 36-Day 92 for RS, ITT, mITT and PP. Severe COVID-19 and death due to COVID-19 by the blinded Independent Adjudication Committee will also be presented.

Number of suspected COVID-19 cases reported from Day 1 to Day 92, those tested with any COVID testing within 14 days after symptoms onset, and Proportion of participants who had COVID testing performed within 14 days after symptoms onset from Day 1 to Day 92 will be presented the Randomized Set.

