## 4 ANALYSIS SETS

### 4.1 Analysis Set Definitions

- **All Screened Participants:** Includes all participants who signed informed consent form. This analysis sets are defined for each Phase of the study as follows:
  - Phase 1/2/3a: this pools data from Phase 1, 2 and 3a participants
  - Phase 3b
  - Phase 3c
  - Pooled: this pools data from Phase 1, 2, 3a and 3b participants
- **Randomized Set (RS):** Includes all participants who are randomly assigned in the study regardless of the participants' vaccination status in the study. Participants will be analyzed according to the vaccine to which the participant was randomly assigned. RS are defined for each Phase of the study as follows:
  - Phase 1/2/3a RS: this pools data from Phase 1, 2 and 3a participants
  - Phase 1 RS
  - Phase 2/3a RS
  - Phase 3b RS
  - Phase 3c RS
  - Pooled RS: this pools data from Phase 1, 2, 3a and 3b participants

Participants who are entered into the unblinded part of IVRS will receive a random ID (randomID). Participants who received a randomID will be entered into the blinded part of the IVRS to receive the treatment assignment. Participants with an assigned randomID but without assigned treatment in the IVRS system will not be considered as randomized.

- **Intent-to-Treat (ITT) Analysis Set:** Includes all participants who receive any dose of study vaccine (ARCT-154 or placebo or ChAdOx1). Participants will be analyzed according to the vaccine to which the participant was randomly assigned. ITT are defined for each Phase of the study as follows:
  - Phase 3b ITT
  - Phase 3c ITT
  - Phase 1/2/3a ITT: this pools data from Phase 1, 2 and 3a participants and will include evaluations up to Day 92 only
  - Pooled ITT: this pools data from Phases 1/2/3a/3b and will include evaluations up to Day 92 only

- **Modified Intent-to-Treat (mITT) Analysis Set:** Includes all participants who received all protocol-required doses of study vaccine (ARCT-154 or placebo or ChAdOx1) up to the evaluation timepoint concerned, and who have no evidence of SARS-CoV-2 infection (no positive RT-PCR or other COVID-19 test or seropositivity for anti-nucleocapsid antibody) on Day 1 or up to 7 days after the 2nd study vaccination. The mITT analysis set will be analyzed according to vaccine assigned. The mITT analysis sets are defined for:
  - Phase 3b mITT
  - Phase 1/2/3a mITT
  - Phase 3c mITT
  - Pooled mITT: this pools data from Phases 1/2/3a/3b and will include evaluations up to Day 92 only

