#### 6.4.1 Primary Efficacy Analysis

The analysis of the first primary endpoint will consider the first occurrence of confirmed, protocol-defined COVID-19 with onset between Day 36 and Day 92 inclusive.

Time at risk = [Last date at risk – (Date received 2nd dose + 7 days)]+1; where the last date at risk will be defined as COVID-19-event date or censor date, whichever comes first.

Summaries of vaccine efficacy will display the number of participants included in the analysis, number of protocol-defined COVID-19 cases (Protocol Appendix 2) and surveillance time in person-year will be summarized in each vaccine group. Surveillance time refers to the total person-time at risk (years) for the given endpoint.

The vaccine efficacy (VE) is defined as the percent reduction in the hazard rate of the COVID-19 events (ARCT-154 versus placebo). The vaccine efficacy is calculated as:

$$VE = 1 - \frac{h_{ARCT-154}}{h_{placebo}} = 1 - HR$$

where  $h_{ARCT-154}$  and  $h_{placebo}$  are hazard rates of the confirmed, protocol-defined COVID-19/Severe COVID-19/death among those in ARCT-154 group and placebo group, respectively.

Vaccine efficacy will be displayed together with 95% confidence interval (CI). Vaccine efficacy is calculated from 1-hazard ratio, where, the hazard ratio (HR) and 95% CI are measured by adjusted Cox proportional hazard regression, with the assumptions of proportional hazards over time. The p-value will be calculated from Cox proportional hazard regression.

Efficacy summaries will also include the proportion of participants with COVID-19 cases in each vaccine group will be displayed together with the Clopper-Pearson 95% CI and a comparison between ARCT-154 and Placebo with 95% CIs. A Log-Rank test p-value will be calculated (in addition to VE% Cox model p-value).

Factors to be used as covariates in Cox proportional hazard regression include:

- Risk group: A randomization stratification factor for age and health risk for severe disease;  $\geq 18$  to  $< 60$  years and “healthy”,  $\geq 18$  and  $< 60$  years and “at risk” and  $\geq 60$  years. Age and health risk at randomization collected in the CRF will be used.
- Study site region: Study site is a randomization stratification factor. However, the sites are grouped into study site region for adjustment factor. Site collected in the CRF will be used.
  - Risk group or study site region will be removed from the model when performing subgroup analysis on that variable.

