### **6.4.3 Exploratory Analysis**

The analysis of exploratory endpoints will follow the same methods of primary analysis and will be performed for Phase 3b and Pooled. Kaplan-Meier plots will be provided for each endpoint.

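### SAP Table 6 starts the clock at dose 1 for the two variant-specific Day 36–92 rows, which inflates displayed surveillance time but leaves vaccine efficacy essentially unchanged

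*SAP*

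**What the plan says.** SAP Table 6 (Section 6.4) gives each efficacy endpoint an analysis set and a time-at-risk formula.

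- **Non-variant Day 36–92 rows** (Primary, Secondary 1, 3 and 4): "Last date at risk – (Date received 2nd dose + 7 days)]+1".
- **Rows counting onset at any time after dose 1** (Secondary 2, Exploratory 1 to 3, and the any-time variant rows): "Last date at risk – Date received 1st dose]+1".
- **Variant-specific Day 36–92 rows**, labelled 4a and 5a in Table 6: the endpoints are "COVID-19 with onset between Day 36 and Day 92 by specific variant" and "Severe COVID-19 with onset between Day 36 and Day 92 by specific variant", the set is mITT, and the formula is the dose-1 one.

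The text under Table 6 fixes the window: "Day 36 is defined as second dose+7 days (29+7=36 days), and Day 92 is defined as second dose+63 days (29+63=92 days". Section 4.1 requires mITT participants to have no evidence of SARS-CoV-2 infection "on Day 1 or up to 7 days after the 2nd study vaccination". Section 6.4.1 has efficacy summaries show person-years by group and explains that "Surveillance time refers to the total person-time at risk (years) for the given endpoint". Section 6.4.3 states that "The analysis of exploratory endpoints will follow the same methods of primary analysis" and asks for a Kaplan-Meier plot for each exploratory endpoint.

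**The concern.** The two variant rows pair a Day 36–92 event definition with a clock that starts on Day 1. Nobody in the mITT set can have a qualifying event before the window opens, so the added days are not time at risk for this endpoint.

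The same mITT participants, followed over the same window, would then appear with one total of person-years in the primary table and a much larger one in the Delta and Omicron tables. A reader who divides cases by person-years would get variant rates that are too low and not comparable with the primary analysis.

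**Working it through.** **Is there an overriding instruction?** Sections 6.4.3.1 to 6.4.3.3 each state a dose-1 formula for their any-time endpoints. Sections 6.4.3.4 and 6.4.3.5, on the variant analyses, state none. The change tables in Section 7 extend the variant analyses and correct their analysis set, but do not mention a different time origin. Table 6 is therefore the only explicit formula for these rows, and it conflicts with the general rule in Section 6.4.3.

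**Inputs**
- Second dose on Day 29, window +2 days (Protocol Appendix 1).
- Window limits (SAP, text under Table 6): 29 + 7 = 36 and 29 + 63 = 92. Both reproduce.
- Censoring no later than completion of the Day 92 visit (SAP 6.4). That visit has a +30-day window in Phase 3b (Protocol Appendix 1), so it can fall as late as Day 122.
- One year = 365.25 days (SAP 5.2).

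**Days contributed by a participant who stays event-free**
- Consistent formula: last day − (dose-2 day + 7) + 1.
- Printed formula: last day − 1 + 1.

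| Dose 2 | Last day | Consistent | Printed | Extra days | Person-time inflated by | Derived rate too low by |
|---|---|---|---|---|---|---|
| Day 29 | 92 | 57 | 92 | 35 | 92/57 − 1 = 61% | 1 − 57/92 = 38% |
| Day 29 | 122 | 87 | 122 | 35 | 122/87 − 1 = 40% | 1 − 87/122 = 29% |
| Day 31 | 92 | 55 | 92 | 37 | 92/55 − 1 = 67% | 1 − 55/92 = 40% |
| Day 31 | 122 | 85 | 122 | 37 | 122/85 − 1 = 44% | 1 − 85/122 = 30% |

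For an illustrative 8,000 participants on schedule and event-free to Day 92, the totals are 8,000 × 57/365.25 = 1,248 person-years against 8,000 × 92/365.25 = 2,015.

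**Effect on the hazard ratio.** One simulated trial was analysed with both origins. The assumptions, which are not in the documents, were 8,000 per arm, dose 2 spread over Days 29–31, a constant placebo hazard of 0.032/57 per day, and half that hazard on vaccine. It gave 355 events.

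| Origin | Placebo, per 1,000 person-years | ARCT-154, per 1,000 person-years | Cox HR |
|---|---|---|---|
| Dose 2 + 7 days | 202.5 | 85.5 | 0.4222 |
| Dose 1 | 123.4 | 52.3 | 0.4221 |

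The rates fall by about 39% in both arms (123.4/202.5 = 0.61; 52.3/85.5 = 0.61). The hazard ratio does not move in any way that matters, because a nearly constant shift of origin with no events in the added period leaves the risk sets almost the same.

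**The case against.** The best defence is that the SAP already points to the right clock. Table 6 is an overview, Section 6.4.3 applies the primary method to exploratory endpoints, and the primary method starts at second dose plus 7 days. Where an exploratory endpoint departs from that, the SAP restates the formula, and for the variant endpoints it restates nothing. On this view the two cells are a copying slip that a careful programmer would resolve correctly. That may be so. But the general rule and the only endpoint-specific formula disagree, and the SAP does not say which governs, so the cells still need correcting.

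Three limits on the consequence stand:

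- A reader might infer immortal-time bias in variant-specific vaccine efficacy. The documents do not support that. The added time is about equal in both arms, efficacy is one minus the Cox hazard ratio, and that ratio is essentially unchanged.
- A reader might infer that a planned incidence result is wrong. Section 6.4.1 lists participants, cases, surveillance time, vaccine efficacy and the proportion with COVID-19, but no rate per person-year. Protocol Section 8.7.3.4 mentions an incidence rate only for the Phase 3b primary endpoint. The proportion does not depend on the clock.
- The endpoints are exploratory and outside the testing hierarchy in Section 6.2.4.

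**Conclusion.** Wrong as written, but minor. The two cells conflict with every other Day 36–92 row and with the method the exploratory analyses are to follow. What is wrong is limited to the displayed surveillance time and the Kaplan-Meier time axis for the variant-specific Day 36–92 analyses.

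With dose 2 on Day 29, person-years are inflated by about 61% if follow-up ends on Day 92 and about 40% if it runs to a Day 92 visit at +30 days. Across the schedule limits examined, a rate that a reader works out from the displayed person-time would be about 29–40% too low. These figures describe participants who remain event-free. The true excess depends on actual second-dose and Day 92 visit dates, which the documents do not give. No conclusion about vaccine efficacy, by variant or overall, changes.

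**What to change.** In the two Table 6 rows for Day 36–92 onset by variant in the mITT set (any COVID-19 and severe COVID-19), replace the dose-1 formula with "Last date at risk – (Date received 2nd dose + 7 days)]+1". Keep the dose-1 formula for the any-time ITT variant rows, where it is right.

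Identify the rows by description, not by label. Table 6 calls the severe Day 36–92 mITT endpoint 5a, whereas SAP Table 2 and Section 7.2 call it 5b and use 5a for the any-time ITT endpoint. A correction made by label from Table 2 would change the sound row and leave the faulty one. Align the 5a/5b labels in the same edit.

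The cost is two table cells, one derivation and a relabelling. No new data or additional analysis is needed.
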